10.4 Deaths

Should a death occur within the study period, or within 60 days after the last administration of investigational product, an adverse event form and an SAE form should be completed, detailing the adverse event that resulted in death (Note: death is an outcome, not an event). The SAE must

be reported to the Medical Monitor within 24 hours of the Investigator becoming aware of the event. The report should contain a comment regarding the co-involvement of progression of disease, if appropriate, and should assign main and contributory causes of death.

10.5 Overdose

The effects of nalbuphine may be reversed with opioid antagonists such as naloxone. Please see the Guidance to the Investigator section of the Investigator's Brochure for additional information.

10.6 Pregnancy

Female subjects who become pregnant should be immediately discontinued from the study if they have not yet received investigational product. If a subject is found to be pregnant after she has received investigational product, she should discontinue dosing, complete all end-of-study procedures, and be followed to determine the outcome of the pregnancy. Generally, follow-up will be no longer than 6 to 8 weeks following the estimated delivery date. While pregnancy itself is not considered an adverse event or SAE, any pregnancy complications or less than a healthy, normal outcome will be recorded as an adverse event or SAE.

10.7 Serious Adverse Events

An SAE is any untoward medical occurrence that, at any dose:

- Results in death
- Is life-threatening
- Requires subject hospitalization or prolongation of existing hospitalization
- Results in persistent or significant disability and/or incapacity
- Results in a congenital anomaly or birth defect

A hospitalization is defined as an inpatient admission lasting 24 hours or more. Visits to urgent care centers and emergency departments that do not result in admission to a hospital for 24 hours will not be considered hospitalizations. Hospitalizations for elective procedures, defined as any procedure that was planned prior to signing of the informed consent will not, in and of themselves, be considered to fulfill criteria for an SAE.

The term "life-threatening" in the definition of "serious" refers to an event in which the subject was at immediate risk of death at the time of the SAE. It does not refer to an SAE that hypothetically might have caused death if it were more severe.

Medical and scientific judgment should be exercised in deciding whether expedited reporting is appropriate in other situations, such as important medical events that may not be immediately life-threatening or result in death or hospitalization, but may jeopardize the subject or may require intervention to prevent one of the other outcomes listed in the definition above. These should also be considered to be SAEs.

10.8 Reporting Serious Adverse Events

Investigators and other site personnel must inform appropriate PAREXEL International Corp. (PAREXEL) representatives of any SAE that occurs (whether or not attributable to the investigational product) in the course of the study within 24 hours of when he or she becomes aware of it.

All SAE reports must be submitted to the following within 24 hours:

PAREXEL International

The PAREXEL representative will work with the Investigator to compile all the necessary information and ensure that the appropriate Sponsor representative receives a report within 1 day (24 hours) for any and all SAEs. Follow-up information on SAEs must also be reported by the Investigator within the same time frames.

11 STATISTICAL EVALUATION

As a companion to this protocol and in an effort to provide a more detailed explanation of the statistical methodology to be used for this study, a statistical analysis plan (SAP) will be developed prior to locking the database and before unblinding the randomization.

11.1 Sample Size and Power

The planned sample size of 44 subjects for the final analysis (22 per sequence) provides at least 80% power to detect a 40% reduction in Day 22 daytime cough frequency (coughs per hour) with NAL ER tablet treatment compared to placebo tablets at the 5% significance level (2-sided). This assumes a CV of 1.00 in log-transformed Day 22 cough frequencies. The CV estimated from *Kelsall et al (2011)* data on chronic cough in patients without esophageal catheterization is 1.12; because Kelsall et al data was on 24-hour cough (including nighttime cough, a period of lower coughing rate) and were not taken in a sample of IPF patients only, it is believed that the CV will be lower than in Kelsall et al data. If the CV is larger than planned at 1.25, this sample size provides > 80% power to detect a 50% reduction from placebo to NAL ER. Alternatively, if the CV is 0.75, this sample size provides > 80% power to detect a 34% reduction from placebo to NAL ER.

A total of approximately 60 subjects will be randomized to ensure complete data from at least 44 subjects, assuming up to potentially a 26% dropout rate.

A statistical update on this Proof-of-Concept (POC) study may be conducted when a minimum of 12 subjects have completed both study periods for the purposes of determining whether POC can be established prior to complete enrollment of the study.

The analysis will be based on conditional power (CP). Futility will be declared if the CP is < 10%, while efficacy will be declared if the CP > 80% (*Mehta and Pocock, 2010*). If the CP is at least 41%, the number of subjects per treatment arm may be changed to recover the targeted power of 80%. If it is evident that the outcome is influenced by a baseline imbalance in disease characteristics then the baseline imbalance will be taken into account in supplemental analyses.

11.2 Statistical Analysis Sets

11.2.1 Safety Population

The safety population will consist of all randomized subjects who have received at least a single dose of investigational product. The safety population will be used in all safety analyses.

11.2.2 Completers Population

The completers population will consist of all subjects who received both study treatments and completed both treatment periods in the study. The completers population will be used in the efficacy analyses.

11.3 Statistical Methods

11.3.1 General Principles

Summary statistics will be presented by treatment group. For continuous variables, unless otherwise stated, the number of available observations (n), mean, standard deviation, median, and range will be provided. For categorical variables, the number and percentage in each category will be displayed.

11.3.2 Missing Data

Missing or dropout data will not be imputed for the purpose of data analysis except for binary "responder" type of efficacy endpoints.

11.4 Demographic and Baseline Characteristics

Demographics and baseline disease characteristics, medical history, laboratory data, and physical examination findings will be summarized descriptively by treatment group.

11.5 Subject Disposition

Subject disposition will be summarized, including the reasons for discontinuation. The number of subjects in each analysis population will be displayed and an accounting of exclusions from each study population will be provided.

11.6 Concomitant Medications

Concomitant medications will be tabulated by Anatomical and Therapeutic Class (ATC) of World Health Organization (WHO) drug, preferred term, and treatment group. A medication's usage will be considered concomitant if it was started or continued after administration of the study medication.

11.7 Analysis of Efficacy Data

The primary efficacy endpoint of percent change in daytime cough frequency (coughs per hour) will be analyzed using a mixed-effects model with sequence, treatment, and time (Day 22) as fixed effects, the baseline value as a covariate, site as a random effect, and subject as a random repeated effect. There will be no imputation for dropouts or missing data for assessments not completed at study visits. A log transformation will be applied to daytime cough frequency; in the presentation of results, log-scale fitted mean treatment group differences at Day 22 will be back-transformed to fitted ratios of geometric means.

As a sensitivity analysis, a negative binomial model will be fitted with the number of coughs at Day 22 as the outcome, with terms for sequence, treatment, and time, as well as baseline cough frequency and subject, and duration of daytime (in hours) as an offset. An autoregressive covariance structure will be assumed for study visits, and the site random effect will use an unstructured covariance matrix.

Secondary efficacy endpoints will be summarized using descriptive statistics. For continuous endpoints (e.g., change from baseline), summaries will include mean, median, standard deviation, minimum, and maximum. For discrete variables (e.g., frequency), summaries will include number of instances and percentage of total instances for that category or time period.

11.8 Analysis of Safety Data

11.8.1 Adverse Events

The incidence of adverse events will be summarized by Medical Dictionary for Regulatory Activities (MedDRA) body system classification and preferred term. All TEAEs will be summarized overall and for each body system and preferred term by treatment group, relationship to investigational product, and severity. For tabulations by severity, only a subject's most severe event within the category (e.g., overall, body system, or preferred term) will be counted. Adverse events will be dichotomized into "related" (probably and possibly) and "unrelated" (unlikely). "Treatment-emergent" will be defined as starting or worsening after the first dose of investigational product. If the start date is missing, the event is assumed to be treatment-emergent. All SAEs will be tabulated.

AESIs that code to the most relevant abuse-related MedDRA preferred terms will be tabulated and descriptive narratives will be written. Additional adverse events that are considered "possibly related to abuse potential" will be tabulated separately.

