5 STUDY OBJECTIVES

5.1 **Primary Objectives**

The primary objectives of this study are as follows:

- To evaluate the safety and tolerability of NAL ER tablets in the study population.
- To evaluate the effect of NAL ER tablets on the mean daytime cough frequency (coughs per hour) at Day 22 (dose 162 mg BID) as compared to placebo. Assessment is done using objective digital cough monitoring. Daytime is defined as the time the subject is awake in the 24 hours after the digital cough monitor is applied for use.

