6 INVESTIGATIONAL PLAN

6.1 Study Design

This is a double-blind, randomized, placebo-controlled, 2-treatment, 2-period crossover efficacy and safety study in IPF subjects with NAL ER tablets for the treatment of cough. The study consists of 2 treatment periods of 3 weeks, each followed by a washout period of 2 weeks.

Treatment Period 1:

During Treatment Period 1, eligible subjects will be randomized (1:1) to one of the following treatment arms:

- Arm 1: Active NAL ER tablets followed by crossover Placebo tablets in Treatment Period 2
- Arm 2: Placebo tablets followed by crossover NAL ER tablets in Treatment Period 2

Following 3 weeks of dosing in Treatment Period 1, subjects will complete a 2-week washout period before entering Treatment Period 2. Subjects assigned to Arm 1 will receive placebo tablets and subjects assigned to Arm 2 will receive NAL ER tablets during Treatment Period 2. A final 2-week washout period will occur at the completion of Treatment Period 2.

NAL ER Dosing

Subjects on NAL ER tablets will have the dose titrated from 27 mg once daily (QD) to 54 mg BID over a 5-day period and then maintained at 54 mg BID for approximately 4 days. Doses will be subsequently escalated and maintained at 108 mg BID over 1 week and then to 162 mg BID over 6 days.

Study Visits:

Study visits will include screening to determine eligibility, and for each treatment period: visits at Day -1 for baseline assessments, at Days 8, 15, and 21 during treatment, and a follow-up at the end of the 2-week washout period. At study screening and the Day 21 visits, during each treatment period, subjects will have blood drawn for safety analysis. Pharmacokinetic (PK) analysis of nalbuphine plasma concentration will also be done at Day 21. Subjects will complete questionnaires for efficacy evaluations and undergo safety evaluations including an ECG. At the baseline and Day 21 visits, during each treatment period, site staff will place an electronic cough monitor on the subject, which will be worn until the evening of the following day in order to obtain at least a full 24-hour recording period of cough frequency. At the end of each recording session, the monitor will be removed at home by the subject prior to bedtime. Subjects will complete a daily e-diary twice per day.

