To mitigate opioid-related side effects, NAL ER tablets will be initiated with a titration schedule. Titration is a clinical management strategy consistent with dosing of opioids in general (*Jovey et al 2003*). In this study, the combination of a low starting dosing (27 mg NAL ER on the first day) followed by a relatively slow titration is expected to minimize treatment-limiting opioid adverse effects.

It is known from prior studies, that GI adverse effects (e.g., nausea and vomiting) and CNS adverse effects (e.g., dizziness, somnolence, and headaches) occur early and can be treatment-limiting. In anticipation of the possible occurrence of these effects, pre-medications for these symptoms will be permitted.

In anticipation of the possible occurrence of CNS AEs such as somnolence, subjects will be instructed to be aware of possible CNS AEs that may occur. The evening doses during the titration period should be taken at home. The first dose of any new titration step will occur with an evening dose (see instructions for taking study medication). Subjects will be instructed that the investigational product may impair mental and/or physical abilities required for the performance of potentially hazardous tasks such as driving a car or operating machinery, especially during the titration period and in combination with alcohol or tranquilizers or other pharmacologic CNS depressants. Subjects will be instructed not to drive or operate machinery unless they are tolerant to the drug and know how they will react to the medication.

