4.2.5 Data Summaries

Subject disposition, Demographics, Medical History, Treatment Exposure and Treatment Compliance tables will be summarized by sequence (see definition in section 4.2.1).

In efficacy and safety tables (including concomitant medications), results will be summarized under the actual treatment received (NAL-ER or Placebo) independently whether the NAL-ER (and Placebo) was received in Treatment Period 1 or 2. In other words, summaries will be presented by treatment received.

In most instances, the baseline visit for Treatment Period 2 will occur on the same calendar day as the Follow-up Visit 6 for Treatment Period 1; in any case, Visit 6 results will be used as Follow-up for Treatment Period 1, while the baseline for the Treatment Period 2 will be the study baseline (taking into account baseline definition from section 4.2.3).

Continuous data will be summarized in terms of the number of subjects with non-missing values, mean, standard deviation (SD), median, minimum and maximum, unless otherwise stated.

The following rules will apply to all descriptive statistic displays, where 'd' denotes the decimal places in the original reported value:

- n (number of non-missing observations): 0 decimal places (d.p.)
- Mean: d + 1 d.p.
- SD: d + 2 d.p.
- Median: d + 1 d.p.
- Minimum: d
- Maximum: d
- Statistics in percentage: 1 d.p.
- Confidence Intervals (CIs): d + 1 d.p.
- A maximum of 3 decimal places will be displayed.

All CIs will be reported as 2-sided and will be assessed at α =0.05 significance level unless otherwise stated.

Categorical data will be summarized in terms of the number of subjects providing data at the relevant time point (n), frequency counts and percentages. The denominator for the proportion will be based on the number of subjects who provided non-missing responses to the categorical variable. Any planned collapsing of categories will be detailed in the SAP text and the data displays.

Percentages will be presented to one decimal place. Percentages will not be presented for zero counts. Percentages will be calculated using n as the denominator.

In general, for categorical variables showing multiple possible categories, these will be displayed following the within variable logic criteria; where such a logic criterium does not exist (example: gender, race, AE SOC, AE PT), categories will be displayed by overall descending frequencies.

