4.12.1.2 Definition of Treatment Emergent Adverse Event (TEAE)

A TEAE is an AE occurring on or after the initial administration of investigational product. In this study, AEs may be treatment emergent with respect to treatment assumed in treatment period 1 or treatment period 2. The following will apply:

- AEs with onset date prior to the date of first of IMP intake in Treatment Period 1 will be considered as AEs non treatment emergent.
- AEs with onset date on or after the date of first IMP intake in Treatment Period 1 (but before first IMP intake in Treatment Period 2) will be considered as Treatment Period 1 TEAE.
- AEs with onset date on or after the date of first IMP intake in Treatment Period 2 will be considered as Treatment Period 2 TEAE.

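### TEAE tables pool both periods by treatment received; supplementary Period 1 tables would show adverse-event incidence as randomised if early attrition differs by treatment

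*Protocol*

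**What the plan says.** Safety is the first-listed primary objective (Protocol 5.1): "To evaluate the safety and tolerability of NAL ER tablets in the study population". The synopsis makes its analysis descriptive, with any inference left to clinical review.

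Protocol 11.8.1 specifies the tables: "All TEAEs will be summarized overall and for each body system and preferred term by treatment group, relationship to investigational product, and severity". It does not mention period. The pooling comes from the SAP. Section 4.12.1.8 sends the TEAE tables to section 4.2.5, which summarises by treatment received, "independently whether the NAL-ER (and Placebo) was received in Treatment Period 1 or 2". None of the tables listed in 4.12.1.8 is split by period, although 4.12.1.2 already labels each event. An onset between the first Period 1 dose and the first Period 2 dose "will be considered as Treatment Period 1 TEAE".

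The safety set requires one dose of either product (SAP 4.5.1). Patients who stop early go to a discontinuation visit and then a follow-up visit (Protocol 6.3.3), and withdrawals are not replaced (7.4). Protocol 6.5 says that gastrointestinal and CNS effects "occur early and can be treatment-limiting". On attrition, Protocol 11.1 states: "A total of approximately 60 subjects will be randomized to ensure complete data from at least 44 subjects". Dropout of up to 26% is allowed for.

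SAP 4.4.1 tabulates early treatment discontinuation by sequence, with the reason and the period.

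**The concern.** A crossover table by treatment received compares like with like when nearly everyone contributes to both columns. A patient in Arm 1 who stops NAL ER in Period 1 contributes events and exposure to the NAL ER column and nothing to the placebo column. The Arm 1 share of the placebo column then consists only of patients who got through NAL ER. If those who stopped were also more likely to report adverse events on placebo, the placebo rate reads low and the excess on NAL ER reads high.

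The protocol gives some reason to expect such attrition. These tables are the main evidence for a primary objective, and no model sits behind them to correct the composition. The Period 1 comparison between randomised arms is free of this selection and of carryover from an earlier treatment. It can be made from the same data but is not planned.

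**Working it through.** **The plan's own figure.** 44 / (1 − 0.26) = 59.5, rounded up to 60, which matches Protocol 11.1. This allows 60 − 44 = 16 non-completers (26.7%). Allocation is 1:1 (Protocol 6.1: "eligible subjects will be randomized (1:1) to one of the following treatment arms"), so about 30 per sequence. The documents do not split dropout by period or treatment.

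**Column sizes.** Let a be the number stopping NAL ER in Period 1 (Arm 1) and b the number stopping placebo in Period 1 (Arm 2). The NAL ER column holds 60 − b patients and the placebo column 60 − a.

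| a | b | NAL ER column | Placebo column | In both | NAL ER only |
|---|---|---|---|---|---|
| 0 | 0 | 60 | 60 | 60 | 0 |
| 4 | 4 | 56 | 56 | 52 | 4 |
| 8 | 4 | 56 | 52 | 48 | 8 |
| 12 | 4 | 56 | 48 | 44 | 12 |
| 16 | 0 | 60 | 44 | 44 | 16 |

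So 0 to 16 patients (0% to 26.7% of the NAL ER column) could appear under NAL ER only.

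**Size of the bias.** Take b = 0. Let Pq be the placebo adverse-event risk in patients who would stop on NAL ER, and P0 the risk in the others.

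- Period 1 placebo rate: P = (a/30)Pq + (1 − a/30)P0
- Pooled placebo rate: [30P + (30 − a)P0] / (60 − a)
- Period 1 minus pooled: (30 − a)(a/30)(Pq − P0) / (60 − a)

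With b = 0 the expected NAL ER rate is the same in both tables, so the last line is also the overstatement of the difference. It is zero if a = 0 or Pq = P0. If b equals a and placebo stoppers are selected in the same way, the NAL ER column shifts too, and the shifts cancel in the difference when the excess risk on NAL ER is the same in stoppers and others.

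The documents give no adverse-event rates. Assuming P0 = 30%, the overstatement in percentage points is:

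| a | Pq = 30% | Pq = 50% | Pq = 70% |
|---|---|---|---|
| 4 | 0 | 1.2 | 2.5 |
| 8 | 0 | 2.3 | 4.5 |
| 16 | 0 | 3.4 | 6.8 |

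Example: a = 8, Pq = 70% gives 22 × (8/30) × 0.40 / 52 = 0.045. If all 16 non-completers stop because of NAL ER, randomisation would lead one to expect about 8 in Arm 1 (Period 1) and 8 in Arm 2 (Period 2). The row a = 8 therefore fits the planned dropout, and a = 16 is an extreme.

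**A second set of assumptions.** Suppose 30% of patients (9 of 30 in Arm 1) are prone to adverse events, with risks of 60% against 30% on placebo and 90% against 60% on NAL ER (prone against not). The true rates are 39% and 69%, a difference of 30 points.

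- 4 stoppers, 60% of them prone: (30 × 0.39 + 6.6 × 0.6 + 19.4 × 0.3) / 56 = 38.4%, an overstatement of 0.6 points.
- 10 stoppers, including all 9 prone patients: (11.7 + 20 × 0.3) / 50 = 35.4%, an overstatement of 3.6 points. Ten prone stoppers are not possible here; the formula without that cap would give 34.8% and 4.2 points.

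**Precision.** At 69% against 39%, the standard error (SE) of a 30 against 30 difference is √(0.2139/30 + 0.2379/30) = 12.3 points. For pooled columns of 60 and 50 it is √(0.2139/60 + 0.2379/50) = 9.1 points, ignoring within-patient correlation. Adding the 3.6-point bias gives √(9.1² + 3.6²) = 9.8, still below 12.3.

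**Denominator.** SAP 4.2.5 does not spell out the adverse-event denominator. With a = 8 and Pq = P0 = 30%, dividing by all 60 treated patients in both columns would make the placebo rate (9 + 6.6)/60 = 26.0% instead of 30.0%. That is 4 points of distortion with no selection at all.

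**The case against.** Tabulating by treatment received is the ordinary safety display for a two-period crossover, and sequence is randomised. With no Period 1 dropout the pooled table is simply the crossover comparison. Safety is descriptive here, the likely error would exaggerate harm and not hide it, and on the figures above the pooled estimate has the smaller total error. Attrition is not concealed either: SAP 4.4.1 shows discontinuations by sequence, reason and period, and adverse-event listings are sorted by sequence with period-specific study days. All of this stands, and it limits the point to a supplement.

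Three stronger readings are tempting, and the documents do not support them:

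- A reader might infer that Protocol 11.8.1 itself prescribes pooling. It says only that tables are by treatment group; the pooling rule is in SAP 4.2.5.
- A reader might infer that the placebo rate will be understated. Protocol 6.5 supports early intolerance of NAL ER, not a raised adverse-event risk on placebo in those who stop. The same mechanism also removes patients who stop placebo in Period 1 from the NAL ER column.
- A reader might conclude that Period 1 should be the reference comparison. Its standard error is about 12 points against about 9, so that would exchange a possible small bias for a certain loss of precision.

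What remains is that no planned table shows adverse-event incidence as randomised. The discontinuation table shows who left and why, not the event rates.

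**Conclusion.** The gap is real but modest. Patients who stop NAL ER in Period 1 enter only the NAL ER column, and no TEAE table is by period. Bias requires both differential Period 1 attrition and a higher background risk in stoppers; neither can be established from the documents. Under assumed risks the overstatement runs from 0 to a few percentage points: 0 to 4.5 with 8 stoppers, and 6.8 only if all 16 planned non-completers stop NAL ER in Period 1 and have a placebo risk of 70% against 30%. The pooled table alone cannot show which case applies. The figures use the planned 30 per sequence. SAP 4.14 and 4.15 record that recruitment ended before the planned total, so the actual columns will be smaller. A supplementary Period 1 table is worth adding because it gives the only as-randomised incidence comparison for a primary objective, from data already collected.

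**What to change.** In SAP 4.12.1.8:

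- Keep the pooled tables as the main display, and state that each column's denominator is the number of patients exposed to that treatment.
- Add supplementary Period 1 tables by treatment, using the label from 4.12.1.2: the TEAE overview, TEAEs by SOC and PT, AESIs, and TEAEs leading to withdrawal of investigational product.
- Optionally, add a table restricted to patients dosed in both periods.
- State that the supplementary tables are read beside the pooled ones when the SAP 4.4.1 discontinuation table shows differential Period 1 attrition, and that they do not replace the pooled tables as the reference.

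The cost is a period filter on tables already specified; no new data are needed. The downside is precision: Period 1 has about half the exposures, at most about 30 against 30 and fewer after the early end of recruitment.
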